7.2 Statistical Methods

Aim 1: Determine the extent to which TSEC reduces anhedonia and other depressive symptoms in PM-MDD. Anhedonia and other depressive symptoms will be assessed at baseline and following 3 weeks of TSEC administration. Null hypothesis (H0): TSEC has no salutary effect on depression. Alternative hypothesis (H1): TSEC reduces depression as evidenced by 1) a statistically significant decrease in average MASQ Anhedonia scale score following 3 weeks of treatment, and 2) a clinically significant increase of 1 SD in MASQ Anhedonia scale score. We will test this hypothesis using a paired t-test of MASQ Anhedonia scores at visit 1 (pre-treatment) and visit 6 (post-treatment).

Aim 2 (Exploratory): Quantify the effect of TSEC on the neural reward system in PM-MDD. We will use fMRI at baseline and following TSEC treatment in PM-MDD to probe frontostriatal reward circuitry. We also will compare the effects of TSEC and ERT in PM-MDD. Null hypothesis (H0): TSEC has no meaningful effect on activity of the neural reward circuit in response to rewards. Alternative hypothesis (H1): TSEC reduces increases neural responsiveness to reward in the frontostriatal reward circuitry as evidenced by increased activation of the caudate, putamen, and nucleus accumbens in PM-MDD in response to reward following TSEC administration (compared with baseline). We will test this hypothesis using a paired t-test to compare activity in 3 regions of interest (ROIs)—caudate, putamen, and nucleus accumbens—at the pretreatment and posttreatment scans.

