Optional Home Visits: In an effort to increase recruitment and retention, the study team will offer home visits for Study Visits 1, 4, 5, as well as Baseline Labs.

Clinical Assessments

The Structured Clinical Interview for DSM-IV-TR Axis-I Disorders (SCID)⁵⁸ and the Schedule for The SCID1 will be administered at baseline to determine study eligibility. The following standard measures will be administered at baseline, both fMRI sessions, and weekly clinic visits:

- The Positive and Negative Affect Schedule⁵⁹ is a 20-item questionnaire that measures both positive affect (PA) and negative affect (NA) and is sensitive to subtle changes in affect over time.
- The Hamilton Rating Scale for Depression (HRSD)⁶⁰ is a 21-item researcher-rated standardized scale that assesses depressive symptoms and is widely used as a measure of symptom change over time.
- The Inventory of Depression and Anxiety Symptoms (IDAS)⁶¹ is a 64-item self-report questionnaire that comprehensively assesses anxiety and depression symptoms on 10 subscales. The IDAS has excellent psychometric properties and has been validated for assessing reproductive mood disorders.
- The Mood and Anxiety Symptom Questionnaire – Anhedonic Depression Subscale (MASQ-AD)⁶² is a 22-item scale that assesses anhedonia (i.e., loss of interest and low positive affect). MASQ-AD scores have been associated with blunted striatal response to reward in previous studies of patients with depression⁶³.
- The Greene Climacteric Scale (GCS)⁶⁴ is a 21-item scale that is the gold-standard measure of four domains of climacteric symptoms: vasomotor, somatic, anxiety, and depression.
- The Pittsburgh Sleep Quality Index (PSQI)⁶⁵ is a 9-item questionnaire that measures the quality and sleep patterns in older adults. *This measure will only be administered at the two fMRI sessions.
- The Hormone History Questionnaire is a 19-item inventory that assesses women's mental and physical health and was created for the purpose of this study.
- The Trauma History Questionnaire¹⁴ is a 24-item measure that examines participant's experiences with potentially serious or traumatic life events.

While the SCID and HAM-D are researcher administered, the other measures will be collected through self-report questionnaires using Qualtrics or paper and pencil questionnaires.

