3.2 Primary Study Endpoints

1. Frontostriatal reactivity to reward during the MID fMRI task
2. Response latency to reward versus non-reward during the MID fMRI task
3. Depressive symptoms

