Aim 1: Determine the extent to which TSEC reduces anhedonia and other depressive symptoms in PM-MDD. Anhedonia and other depressive symptoms will be assessed at baseline and following 3 weeks of TSEC administration.

Null hypothesis (H_0): TSEC has no salutary effect on depression.

Alternative hypothesis (H_1): TSEC reduces depression as evidenced by 1) a statistically significant decrease in average MASQ Anhedonia scale score following 3 weeks of treatment, and 2) a clinically significant increase of 1 SD in MASQ Anhedonia scale score.

We will test this hypothesis using a paired t-test of MASQ Anhedonia scores at visit 1 (pre-treatment) and visit 6 (post-treatment).

Aim 2 (Exploratory): Quantify the effect of TSEC on the neural reward system in PM-MDD. We will use fMRI at baseline and following TSEC treatment in PM-MDD to probe

frontostriatal reward circuitry. We also will compare the effects of TSEC and ERT in PM-MDD.

Null hypothesis (H_0): TSEC has no meaningful effect on activity of the neural reward circuit in response to rewards.

Alternative hypothesis (H_1): TSEC reduces increases neural responsiveness to reward in the frontostriatal reward circuitry as evidenced by increased activation of the caudate, putamen, and nucleus accumbens in PM-MDD in response to reward following TSEC administration (compared with baseline).

We will test this hypothesis using a paired t-test to compare activity in 3 regions of interest (ROIs)—caudate, putamen, and nucleus accumbens—at the pretreatment and posttreatment scans.

2. The principal investigator will evaluate the progress of the trial, including periodic assessments of data quality and timeliness, participant recruitment, accrual and retention, participant risk versus benefit, performance of the trial site, and other factors that can affect study outcome.

B. Measures taken to insure data integrity and protection of databases

1. All study personnel are responsible for the collection and storage of data. All study staff participate in annual human subject training that includes education about responsibilities to minimize risk that confidentiality may be breached.

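### Aim 1 draws a conclusion about depression from an anhedonia scale alone, and other depressive symptoms have no planned efficacy analysis although HRSD and IDAS are collected

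*Combined protocol and SAP*

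**What the plan says.** Aim 1 has two parts: "Determine the extent to which TSEC reduces anhedonia and other depressive symptoms in PM-MDD". It appears in the Study Summary, section 2, section 7.2 and Appendix A (V.A.1.b). The null hypothesis concerns depression as a whole: "TSEC has no salutary effect on depression". The alternative is equally broad, but its evidence is one scale: "TSEC reduces depression as evidenced by 1) a statistically significant decrease in average MASQ Anhedonia scale score following 3 weeks of treatment". The second criterion, a 1 SD criterion, uses the same scale. The analysis is a single sentence: "We will test this hypothesis using a paired t-test of MASQ Anhedonia scores at visit 1 (pre-treatment) and visit 6 (post-treatment". The Study Summary names the same test and no other for this hypothesis.

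The clinical assessments in section 3.1 separate the instruments. MASQ-AD "is a 22-item scale that assesses anhedonia (i.e., loss of interest and low positive affect", whereas HRSD "is a 21-item researcher-rated standardized scale that assesses depressive symptoms and is widely used as a measure of symptom change over time". IDAS is described there as covering anxiety and depression on 10 subscales. HRSD (listed as HAM-D) and IDAS are marked at visits 1, 3, 4, 5 and 6 in Table 1 and in the Appendix A schedule.

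Section 3.2 gives the third primary endpoint as "Depressive symptoms", with no instrument and no time point.

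**The concern.** The conclusion is broader than the test behind it. Aim 1 itself distinguishes anhedonia from other depressive symptoms, and only anhedonia is analysed. Two misleading results are possible under the plan as written:

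- MASQ-AD falls and HRSD and IDAS do not move, yet the alternative, worded as a reduction in depression, may be declared.
- HRSD falls and MASQ-AD does not, so the null of no benefit for depression is retained.

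This matters because section 1.1 presents the study as a test of the drug's antidepressant effect and of whether it can be used to treat perimenopausal MDD. There is also a selection risk. With an unnamed primary endpoint and three candidate scales, nothing in the plan stops the reported scale from being chosen after the data are seen.

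**Working it through.** **Does any passage supply the missing analysis?**

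- Sections 2 and 7.2 and Appendix A V.A.1.b: the MASQ Anhedonia paired t-test is the only Aim 1 analysis. The other tests are the Aim 2 comparisons in three brain regions.
- Section 3.2: the endpoint is listed without an instrument.
- Sections 4.4.1 and 8.5 and Appendix A III.C: HRSD is used for discontinuing individual women. Section 8.6 lists HRSD and IDAS among the scales used in medical monitoring. These are safety uses.

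No efficacy analysis of HRSD or IDAS appears. MASQ-AD has no row in either schedule table, although the section 3.1 text lists it among the repeated measures.

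**The plan's own power figure.** Section 7.1 gives 80% power for an effect of 0.7 in 20 women. Alpha and sidedness are not stated; I assume two-sided 0.05. For a paired t-test, df = n − 1 and the noncentrality is d√n.

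- n = 20, d = 0.7: 0.7 × √20 = 3.13 on 19 df, exact power 84.4%.
- Smallest n for 80% power: 19.
- Effect detectable with 80% power at n = 20: 0.66.

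The stated size of 20 is therefore sound for one paired test.

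**What requiring HRSD as well would cost.** The documents give no standardised change for HRSD, so it must be assumed. For two tests with powers p1 and p2, the chance that both succeed lies between p1 + p2 − 1 and the smaller of the two. With MASQ-AD at 0.7 (84.4%) and 20 women analysed:

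| Assumed HRSD change | HRSD power | Both succeed |
|---|---|---|
| 0.5 | 56.5% | 0.844 + 0.565 − 1 = 41% to 57% |
| 0.7 | 84.4% | 2 × 0.844 − 1 = 69% to 84% |
| 1.15 | 99.8% | 0.844 + 0.998 − 1 = 84% (upper limit also 84%) |

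If the two tests were independent, the 0.7 row would give 0.844² = 71%. With 16 rather than 20 women analysed, power at 0.7 is 74.5% per test.

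**Why a fixed order.** Splitting alpha equally over two tests (0.025 each) would cut power at 0.7 to 75.2% per test. Testing MASQ-AD first at 0.05, and HRSD only after a significant MASQ-AD result, leaves MASQ-AD at 84.4%.

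**Size of the selection risk.** If scales were tested at 0.05 each without correction and were independent, the chance of at least one false positive would be 1 − 0.95² = 9.8% for two scales and 1 − 0.95³ = 14.3% for three. Positive correlation would lower both figures.

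**The case against.** The strongest reply is that the plan does say how depression will be judged. The alternative makes MASQ Anhedonia the evidence, the instrument's full name is the Anhedonic Depression Subscale, and section 1.1 treats anhedonia as a cardinal feature of depression. This stands to the extent that a reader might infer that depression goes wholly untested, and the documents do not support that. It is tested through a narrow proxy. The reply does not reach the other depressive symptoms, which have no efficacy test at all.

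A reader might also infer that the HRSD and IDAS data sit idle. They do not: both serve monitoring, and HRSD also serves discontinuation. What is missing is an efficacy analysis.

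Nor do the documents show that the prior effect in section 7.1 came from a scale other than MASQ-AD. That section refers only to depressive and mood symptoms and names no instrument.

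HRSD has weaknesses of its own as an efficacy measure. Women scoring above 20 are to be discontinued (4.4.1, 8.5, Appendix A III.C), and only protocol-compliant women are analysed (7.3), so women who worsen may leave the analysis and the mean may appear to fall. After discontinuation only self-report ratings continue (4.4.2), whereas HRSD is researcher administered, by study staff in an unblinded study. This argues for stating the limitation and adding a self-report scale; it does not justify leaving the endpoint without an analysis.

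Finally, this is a 20-woman pilot for a larger placebo-controlled study (section 1.1). Limiting the conclusion to anhedonia and reporting HRSD and IDAS descriptively would remove the mismatch. That is a reasonable minimum, but the study would then give up its depression claim.

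**Conclusion.** The point holds as a mismatch between claim and test. Aim 1 and its hypotheses concern depression, the only analysis concerns anhedonia, and the remaining depressive symptoms have no efficacy analysis although suitable data are scheduled at five visits. It should be corrected before the data are analysed. It makes no stated figure wrong: 20 women gives 84% power at 0.7 for one paired test.

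It would be tempting to add that HRSD and IDAS have the same power as MASQ-AD. That is true only if each has a standardised change of 0.7, which the documents do not give. On that assumption, with two-sided alpha 0.05 and all 20 women analysed, both tests succeed with probability 69% to 84%, so the broad claim can lose up to about 15 points of power.

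**What to change.** In section 2, section 7.2 and Appendix A V.A.1.b, with the Study Summary and section 3.2 brought into line:

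1. Reword the alternative so that the MASQ-AD test supports a claim about anhedonia only.
2. Name HRSD total as the measure of other depressive symptoms. Report its mean change from the same baseline (visit 1) to visit 6 with a 95% CI whatever the MASQ-AD result. Place the formal HRSD test second in a fixed order.
3. Pre-name one IDAS depression score as supportive. Note that self-report ratings continue after discontinuation, whereas HRSD is researcher administered.
4. Allow the statement that TSEC reduces depression only if HRSD also falls.
5. State as a limitation that HRSD-based discontinuation combined with a compliant-only analysis can favour an apparent HRSD fall.

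MASQ-AD should also be given a row in both schedule tables.

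The cost is a few sentences, with no added women or visits. The broad claim becomes harder to reach, as quantified above. One gap remains: if MASQ-AD is not significant, HRSD gets an estimate and interval but no confirmatory test. That is the price of keeping full alpha for MASQ-AD, and reporting the interval in every case keeps a fall in HRSD visible.

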Conjugated estrogens/bazedoxifene	0.45 milligrams/20 milligrams/day	Oral tablet						

	Drug	Route of Administration
	Conjugated estrogens/bazedoxifene	Oral
Regimen:		
Once determined eligible and physically well, participants with perimenopausal depression will receive a tissue selective estrogen complex (TSEC) (conjugated estrogens/bazedoxifene, 0.45mg/20mg) for 3 weeks. Prior to beginning medication, women will have a basic lab panel and serum pregnancy test, pelvic exam, breast exam, and PAP smear. Participants who can provide record of a pelvic exam and breast exam within the past year and normal pap results within the past three years will be permitted to decline the GYN exam. Women will be seen in the clinic each week during TSEC administration to assess blood levels of estradiol and mood symptoms.		
Duration of administration	3 weeks	
Reference population	Perimenopausal women, non-depressed	
Statistical Methodology:	We will test our H1 hypothesis using a paired t-test of MASQ Anhedonia scores at visit 1 (pre-treatment) and visit 6 (post-treatment). We will test our H2 hypothesis using a paired t-test to compare activity in 3 regions of interest (ROIs)—caudate, putamen, and nucleus accumbens—at the pretreatment and posttreatment scans.	

1 Introduction

This document is a protocol for a human research study. This study is to be conducted according to US and international standards of Good Clinical Practice (FDA Title 21 part 312 and International Conference on Harmonization guidelines), applicable government regulations and Institutional research policies and procedures.

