7.1 Sample Size Determination

The researchers will have 80% power to detect a large effect size (.7) in 20 women. Our recently completed study of the effects of transdermal estradiol on mood symptoms in the same population showed a reduction in depressive symptoms with the PM-MDD group from pre-treatment to post-treatment ($t=4.3$, $p<0.001$ Cohen's $d=1.15$). We anticipate the TSEC (the active ingredient of which is estrogen) to have similar effects on mood symptoms, and thus, the sample size of 20 is a conservative estimate of the number of subjects we will need to detect a statistically significant effect.

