We will have 80% power to detect a large effect size (.7) in 20 women. Our recently completed study of the effects of transdermal estradiol on mood symptoms in the same population showed a reduction in depressive symptoms with the PM-MDD group from pre-treatment to post-treatment ($t=4.3$, $p<0.001$ Cohen's $d=1.15$). We anticipate the TSEC (the active ingredient of which is estrogen) to have similar effects on mood symptoms, and thus, the sample size of 20 is a conservative estimate of the number of subject we will need to detect a statistically significant effect.

B. Safety and study progress reviews

1. The research coordinator will evaluate the study subjects at appropriate intervals and assess laboratory data and clinical signs for potential adverse events. The research coordinator will assist the PI with gathering information to help the PI determine classification and causality. The research coordinator will also observe and document all adverse events, act on the PI's recommendation, and maintain follow-up until reconciliation.
2. The principal investigator and [name] will review the adverse events, immediately after they occur, with follow-up resolution. The principal investigator and [name] will evaluate individual and cumulative participant data when making recommendations regarding the safe continuation of the study. The principal investigator will be notified within 24 hours of an adverse event.
3. Specific responsibilities of the principal investigator include:
 - a. Review the research protocol, informed consent documents, and plans for data safety and monitoring;
 - b. Evaluate the progress of the trial, including periodic assessments of data quality and timeliness, participant recruitment, accrual and retention, participant risk versus benefit, performance of the trial site, and other factors that can affect study outcome;
 - c. Consider factors external to the study when relevant information becomes available, such as scientific or therapeutic developments that may have an impact on the safety of the participants or the ethics of the trial;
 - d. Protect the safety of the study participants;
 - e. Report on the safety and progress of the trial;
 - f. Make recommendations to the UNC-CH IRB, and, if required to the Food and Drug Administration (FDA) concerning continuation, termination, or other modifications of the trial based on the observed beneficial or adverse effects of the treatment under study;

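### The Aim 1 hypothesis requires both a significant fall and a 1 SD rise in the same anhedonia score, and leaves the SD, the level and the role of the 1 SD criterion undefined

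*Combined protocol and SAP*

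**What the plan says.** Section 7.2 gives the Aim 1 alternative hypothesis in two numbered parts joined by *and*. Part 1 is "TSEC reduces depression as evidenced by 1) a statistically significant decrease in average MASQ Anhedonia scale score following 3 weeks of treatment". Part 2 is "a clinically significant increase of 1 SD in MASQ Anhedonia scale score". Section 2 and Appendix A V.A.1.b repeat the same two parts.

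The direction of benefit is clear elsewhere. The aim is to "Determine the extent to which TSEC reduces anhedonia and other depressive symptoms in PM-MDD", and Section 3.1 says the MASQ-AD "is a 22-item scale that assesses anhedonia (i.e., loss of interest and low positive affect").

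The only analysis named for the hypothesis is a paired t-test of visit 1 against visit 6, in each of the three places and in the Study Summary. The Study Summary does not mention the 1 SD part. On sample size, Section 7.1 says "The researchers will have 80% power to detect a large effect size (.7) in 20 women", and Appendix A III.A says the same.

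**The concern.** A higher score on a scale of anhedonia is worse, so part 2 as written makes a deterioration evidence of benefit. If both parts apply to the group mean, no data can satisfy them.

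Reversing the direction leaves three questions that the plan does not answer:

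- **Which SD?** It could be the SD of visit 1 scores, of the change scores, or of some reference sample. No value is given.
- **Which level?** Part 1 refers to the average; part 2 names no level. If it applies to each woman, no required share of women is given.
- **What role?** The word *and* suggests that both parts are needed. The named test can judge only part 1.

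Aim 1 is the only aim not labelled exploratory, and this is its success rule. A significant fall of less than 1 SD could be reported as support or as failure, and the choice could be made after the data are seen. The study is single-arm and unblinded, which makes a success rule fixed in advance more important.

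**Working it through.** **Inputs.** n = 20 and effect size 0.7 (Section 7.1). The reference effect d = 1.15 is also from Section 7.1; it comes from the earlier transdermal estradiol study and concerns depressive symptoms, with MASQ not named. Assumptions: two-sided alpha 0.05 (the plan states neither alpha nor sidedness), normally distributed changes, d = mean change / SD of change, and equal SDs at the two visits.

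**1. The plan's own figure.** For a paired t-test, df = 19 and the noncentrality is d × √20. At d = 0.7 this is 3.13, and the power is 84.4%. The smallest n giving 80% power is 19, so the stated 20 is sound for part 1. At d = 1.15 the power is 99.8%. One-sided 0.05 gives 91.5% at d = 0.7.

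**2. As written, for the group mean.** Part 1 needs a mean change below zero and part 2 needs one of at least +1 SD. The chance of meeting both is 0 whatever the true effect.

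**3. Direction reversed, both parts required of the mean, SD of change.** Significance needs an observed fall of t(0.975, 19)/√20 = 2.093/4.472 = 0.468 SD. A fall of at least 1 SD means t ≥ √20 = 4.472, which already implies significance. So the joint chance is P(t ≥ √20) with noncentrality d × √20:

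- d = 0.7: 14.9%
- d = 1.15: 72.4%

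These two figures are the same for a one-sided test at 0.05, because the 1 SD mark is the stricter condition.

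The chance of a significant fall short of 1 SD (observed fall between 0.47 and 1.0 SD) is the difference:

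- d = 0.7: 84.4% − 14.9%, about 69%
- d = 1.15: 99.8% − 72.4%, about 27%

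**4. The same rule with the visit 1 SD.** One visit 1 SD equals 1/√(2(1 − r)) SDs of change, where r is the correlation between visits. The plan gives no r, so a range is shown. The sample-SD columns come from 400,000 simulated trials per cell, using each trial's observed visit 1 SD as the threshold. The known-SD columns treat that SD as fixed (300,000 simulated trials).

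| r | d = 0.7, sample SD | d = 0.7, known SD | d = 1.15, sample SD | d = 1.15, known SD |
|---|---|---|---|---|
| 0 | 50% | not run | 96% | not run |
| 0.3 | 31% | 26% | 89% | 91% |
| 0.5 | 15% | 9% | 72% | 75% |
| 0.7 | 3% | 0.4% | 35% | 27% |
| 0.8 | 0.5% | not run | 11% | not run |

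**5. Per-woman reading, d = 0.7, SD of change.** The share rising by at least 1 SD is Φ(−1.7) = 4.5%. The share falling by at least 1 SD is 1 − Φ(0.3) = 38%. With the visit 1 SD, the share falling is 44%, 38% or 28% at r = 0.3, 0.5 or 0.7.

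**The case against.** The strongest reply is that *increase* is an obvious slip. Part 1, the aim and the opening of the hypothesis all point to a reduction, and no analyst would count a 1 SD rise in anhedonia as success. On this view the 0% result and the 4.5% of women describe a rule nobody would apply. It can be added that the paired t-test follows the hypothesis each time and the study is sized for a statistically significant effect, so the natural reading is that the t-test decides and 1 SD is a benchmark. The two-part powers would then not apply. Finally, those powers rest on an assumed alpha and an assumed correlation, and the study is a pilot of 20 women.

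Much of this stands. The intended direction is hardly in doubt, the impossibility result should not carry the weight of the point, and the two-part powers are conditional on a reading. The stated sample size is not at fault. What remains is that the hypothesis names two pieces of evidence joined by *and*, and nothing says that the second is only a benchmark. A reader who corrects the slip still has no SD, no level and no role for it. The figures depend on assumptions, but at the planning effect every two-part version shown falls well below 84%.

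**Conclusion.** The point holds: the Aim 1 criterion is wrong as written, and the likely one-word correction does not complete it. The plan's sample size reproduces for the significance test and says nothing about a 1 SD criterion. At the planning effect of 0.7, the chance of success is 84% if the t-test decides. If both parts are required of the mean, it is 15% with the SD of change, and between 0.4% and 50% with the visit 1 SD, depending on the correlation and on how that SD is obtained. At 1.15 the t-test figure is 99.8%, against 72% with the SD of change and 11% to 96% with the visit 1 SD. These figures assume two-sided 0.05 and normal changes. The contradiction in direction and the missing definitions rest on the text alone. The rule should be settled before the data are seen.

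**What to change.** In Section 2, Section 7.2 and Appendix A V.A.1.b:

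1. Change *increase* to *decrease* in part 2.
2. State which SD is meant, and whether it applies to the mean change or to individual women. If to individual women, say how it will be summarized.
3. State that the paired t-test of mean change decides the hypothesis, and that the 1 SD decrease is a clinical benchmark reported beside the mean change and its 95% confidence interval. This agrees with the Study Summary.

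If the sponsor wants both parts to be required, say so explicitly. In that case add to Section 7.1 and Appendix A III.A that the 80% power at 0.7 covers the significance test only, and give the power of the two-part rule for the chosen SD. For the SD of change applied to the mean, this is about 15% at 0.7 and 72% at 1.15. For the visit 1 SD, give the figure at a stated correlation.

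The cost is one word and one or two sentences in three places, plus one sentence in each sample size section only if both parts are required. No extra participants, visits or data are needed.
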